### **6.3 Measures to Minimize Bias: Randomization and Blinding**

#### **6.3.1 Intervention Assignment**

This is an open-label study. Study intervention assignment will occur centrally using an interactive response technology system.

#### **6.3.2 Stratification**

No stratification based on age, sex, or other characteristics will be used in this study.

#### **6.3.3 Blinding**

This is an open-label study; therefore, the Sponsor, investigator, and participant will know the intervention administered.

### **6.4 Study Intervention Compliance**

Interruptions from the protocol-specified treatment for  $\geq 12$  weeks for selumetinib doses for non-drug related or administrative reasons require consultation between the investigator and the Sponsor and written documentation of the collaborative decision on participant management.

### **6.5 Concomitant Therapy**

Medications or vaccinations specifically prohibited in the exclusion criteria are not allowed during the ongoing study. If there is a clinical indication for any medications or vaccinations specifically prohibited, discontinuation from study intervention will be required.

#### **6.5.1 Acceptable Concomitant Medication**

All treatments that the investigator considers necessary for a participant's welfare may be administered at the discretion of the investigator in keeping with the community standards of medical care except for those that are prohibited as described in Section 6.5.2. All concomitant medication will be recorded on the case report form (CRF) including all prescription, over-the-counter, herbal supplements, and IV medications and fluids. If changes occur during the study period, documentation of drug dosage, frequency, route, and date may also be included on the CRF.

Of note, selumetinib can be administered with caution in participants who are receiving concomitant coumarin anticoagulant medications, eg, warfarin. These participants should have their INR monitored, anticoagulant assessments conducted more frequently, and the dose of the anticoagulant therapy adjusted accordingly.

All concomitant medications received within 28 days before the first dose of study intervention and 30 days after the last dose of study intervention should be recorded. Concomitant medications administered after 30 days after the last dose of study intervention should be recorded for SAEs and ECIs as defined in Section 8.4.

## 6.5.2 Prohibited Concomitant Medications

Participants are prohibited from receiving the following therapies during the Screening and Treatment Phases of this study:

- Antineoplastic systemic chemotherapy or biological therapy
- Immunotherapy not specified in this protocol
- Chemotherapy not specified in this protocol
- Investigational agents other than selumetinib (MK 5618) and pembrolizumab (MK-3475).
- For agents that may affect the metabolism of selumetinib (eg, strong inhibitors and inducers of CYP2C19 or CYP3A4), caution should be taken. However, changes in exposure of selumetinib with strong inhibitors/inducers would be moderate based on clinical evidence (1.5-fold).
- Participants should not take any supplemental vitamin E. High doses of vitamin E have been reported to cause bleeding and interrupt blood coagulation processes.

Note: Selumetinib capsules contain vitamin E in the form of D-a-tocopheryl polyethylene glycol 1000 succinate (TPGS), a water-soluble form of vitamin E, which acts as a formulation excipient.

- Radiation therapy

Note: Radiation therapy to a symptomatic solitary lesion or to the brain may be allowed at the investigator's discretion after the DLT observation period.

- Live vaccines within 28 days prior to the first dose of study intervention and while participating in the study. Examples of live vaccines include, but are not limited to the following: measles, mumps, rubella, varicella/zoster, yellow fever, rabies, Bacillus Calmette–Guérin, and typhoid vaccine. Seasonal influenza vaccines for injection are generally killed virus vaccines and are allowed; however, intranasal influenza vaccines (eg, FluMist®) are live attenuated vaccines and are not allowed.
- Systemic glucocorticoids for any purpose other than to modulate symptoms from an AE of suspected immunologic etiology. The use of physiologic doses of corticosteroids may be approved after consultation with the Sponsor.

Participants who, in the assessment by the investigator, require the use of any of the aforementioned treatments for clinical management should be removed from the study. Participants may receive other medications that the investigator deems to be medically necessary.

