#### Nausea and/or vomiting

Because nausea and vomiting have been reported for selumetinib, it is recommended that participants are educated on the possibility of occurrence of these side effects prior to starting study treatment. Participant education as well as proper management of nausea and/or vomiting at the first sign is important. Clinical judgment and experience of the treating physician should guide the management plan of each participant. Participants experiencing nausea and/or vomiting CTCAE Grade  $\geq 1$  should receive antiemetics at the discretion of the treating physician (as per local guideline). It is recommended that participants be provided a prescription for antiemetics and are instructed on the use of antiemetics on the first day of study drug treatment. Prophylactic antiemetics such as dexamethasone 8 mg, prochlorperazine, metoclopramide, ondansetron, or aprepitant may be administered to participants on an "as needed" basis. Medication use should be recorded accordingly.

Dose interruption/reduction decisions for nausea and/or vomiting should be based on the CTCAE grade of the toxicity and the guidelines provided in Section 6.6.1.

As guidance for recommendations on supportive measures for the prevention and/or management of nausea and/or vomiting, the published recommendation from ASCO [Sepulveda, A. R., et al 2017], ESMO [Van Cutsem, E., et al 2016], and Multinational Association of Supportive Care (MASCC) can be used [Basch, E., et al 2011] [Roila, F., et al 2010].

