## Skin Toxicity

Clinical judgment and experience of the treating physician should guide the management plan of each participant. In general, the following interventions are in addition to the rash dosing adjustment guidelines in [Table 5](#) Dose Modification and Toxicity Management Guidelines for Immune-related Adverse Events Associated with Pembrolizumab Monotherapy, Coformulations or IO Combinations:

- Prophylaxis of skin toxicity to be initiated 24 hours prior to the first treatment with study drug or later as needed.
- Application of topical agents to the most commonly affected skin areas such as face, scalp, neck, upper chest and upper back.

Topical agents include non-oily sunscreen (para-aminobenzoic acid free, SPF  $\geq 30$ , ultraviolet A/ultraviolet B protection), topical steroids (preferably mometasone cream, ie, Elocon®) and topical erythromycin (ie, Eryaknen® or topical pimecrolimus).

**Note:** Topical agents should be applied on a daily basis starting on Day 1 of study treatment or 24 hours prior to the first dose, and more often as needed.

- Possibly oral doxycycline (100 mg daily) for the first 2 to 3 weeks of study drug administration.

Other effective medications are antihistamines, other topical corticosteroids, other topical antibiotics and low-dose systemic corticosteroids.

The treatment algorithm based on CTCAE grade is as follows:

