### **Severe rash (CTCAE Grade 3 to 4)**

#### **CTCAE Grade 3**

- In addition to the interventions recommended for moderate rash, consider oral prednisolone at a dose of 0.5 mg/kg. Upon improvement, taper the dose in a stepwise manner (25 mg for 7 days, subsequently decreasing the dose by 5 mg/day every day).
- Alternatively, in addition to the interventions recommended for moderate rash, consider oral isotretinoin (low doses, ie, 0.3 to 0.5 mg/kg) [Lacouture, M. E., et al 2011].
- Use of acitretin is not recommended.

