## **6.6 Dose Modification (Escalation/Titration/Other)**

### **6.6.1 Dose Modifications Due to Adverse Events**

In previous studies of selumetinib and pembrolizumab monotherapy, overlapping toxicities have been observed for selumetinib and pembrolizumab (refer to IBs). These overlapping toxicities include pneumonitis, diarrhea/colitis, cardiac function decrease, and skin rash.

In the current study, the relationship of these AEs to selumetinib and/or pembrolizumab may be difficult to unambiguously assign. Therefore, if a participant experiences an AE related to either treatment, both selumetinib and pembrolizumab will be modified or discontinued as described in [Table 4](#) and [Table 5](#).

If 2 different therapies are proposed in these tables, the most conservative/effective treatment should be chosen (ie, steroid). Further, if the investigator believes the treatment emergent toxicity is unambiguously related to only one of the agents, they may continue the participant on the unrelated agent following consultation with the Sponsor.

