### 6.6.2.2 Definition of Dose-limiting Toxicity

All toxicities will be graded using NCI CTCAE Version 4.0 based on the investigator assessment. The DLT window of observation will be during first 21-days of treatment.

The occurrence of any of the following toxicities will be considered a DLT, if assessed by the investigator to be possibly, probably or definitely related to study drug administration, excluding toxicities clearly not related to the drug, such as disease progression, environmental factors, unrelated trauma:

1. Grade 4 non-hematologic toxicity (not laboratory).
2. Hematologic toxicity:
  - Grade 4 neutropenia  $>5$  days
  - Grade 4 thrombocytopenia of any duration
  - Grade 3 thrombocytopenia with clinically significant bleeding
  - Other Grade 4 hematologic toxicity lasting  $\geq 7$  days
3. Any non-hematologic AE Grade 3 severity (not laboratory) should be considered a DLT, with the following exceptions:
  - Grade 3 fatigue lasting  $\leq 3$  days
  - Grade 3 diarrhea, nausea, or vomiting lasting  $<72$  hours in the absence of maximal medical therapy
  - Grade 3 rash without use of corticosteroids or anti-inflammatory agents per standard of care
4. Any Grade 3 or Grade 4 non-hematologic laboratory value if:
  - Clinically significant medical intervention is required to treat the participant, or
  - The abnormality leads to hospitalization, or
  - The abnormality persists for  $>1$  week
  - The abnormality results in a Drug-induced Liver Injury (DILI) (see Sections 8.4.1 and 8.4.7 for criteria).

Examples of some exceptions: Clinically nonsignificant, treatable, or reversible laboratory abnormalities include liver function tests, urine acid.

5. Febrile neutropenia Grade 3 or Grade 4:

- Grade 3 is defined as absolute neutrophil count  $<1000/\text{mm}^3$  with a single temperature of  $>38.3^\circ\text{C}$  ( $101^\circ\text{F}$ ) or a sustained temperature of  $\geq38^\circ\text{C}$  ( $100.4^\circ\text{F}$ ) for more than 1 hour.
- Grade 4 is defined as absolute neutrophil count  $<1000/\text{mm}^3$  with a single temperature of  $>38.3^\circ\text{C}$  ( $101^\circ\text{F}$ ) or a sustained temperature of  $\geq38^\circ\text{C}$  ( $100.4^\circ\text{F}$ ) for more than 1 hour, with life-threatening consequences and urgent intervention indicated.

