6. An elevated AST or ALT lab value that is  $\geq3X$  the upper limit of normal and an elevated total bilirubin lab value that is  $\geq2X$  the upper limit of normal and, at the same time, an alkaline phosphatase lab value that is  $<2X$  the upper limit of normal, as determined by way of protocol-specified laboratory testing or unscheduled laboratory testing.
7. Any prolonged delay ( $>2$  weeks) in initiating Cycle 2 study treatment due to a treatment-related toxicity.
8. Any treatment-related toxicity that causes the participant to discontinue treatment during Cycle 1.
9. Missing  $>25\%$  of selumetinib doses as a result of drug-related AE(s) during the first treatment cycle.

10. Grade 5 toxicity

11. Cardiac disorders

- Absolute decrease in LVEF  $>10\%$  compared with baseline and the LVEF is below the institution's lower limit of normal
- Left ventricular systolic dysfunction Grade  $\geq3$
- Other cardiac disorders Grade  $\geq3$

12. Vascular disorders

- Hypertension CTCAE Grade  $\geq3$  requiring more than 1 drug or more intensive therapy
- Grade 4 hypertension

13. Eye disorders

- Retinopathy or retinal detachment Grade  $\geq3$ , confirmed by ophthalmic examination

- Retinal vein disorder including RVO, confirmed by ophthalmic examination
- Visual disturbances without ocular (retinal) changes
- Blurred vision, flashing lights, floaters: Grade  $\geq 3$
- Other (not listed above)
- Grade  $\geq 3$  for  $>21$  consecutive days
- Grade 4 confirmed by ophthalmic examination

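### Section 6.5.2 bars systemic steroids outside suspected immunologic AEs, yet Section 6.5.3.1 offers dexamethasone as an antiemetic; how a resulting Cycle 1 removal enters the DLT count is not stated

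*Combined protocol and SAP*

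**What the plan says.** **The ban.** Section 6.5.2 lists, among therapies prohibited during screening and treatment, "Systemic glucocorticoids for any purpose other than to modulate symptoms from an AE of suspected immunologic etiology". The only other allowance is for physiologic doses with the sponsor's agreement. Participants who, in the investigator's assessment, "require the use of any of the aforementioned treatments for clinical management should be removed from the study". Section 6.5.1 leaves other treatment to the investigator's discretion but keeps the Section 6.5.2 list outside that discretion.

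**The supportive-care text.** Section 6.5.3.1 (selumetinib) says on nausea: "Prophylactic antiemetics such as dexamethasone 8 mg, prochlorperazine, metoclopramide, ondansetron, or aprepitant may be administered to participants", as needed. It also recommends giving an antiemetic prescription on the first day of study drug. On skin toxicity it says: "Other effective medications are antihistamines, other topical corticosteroids, other topical antibiotics and low-dose systemic corticosteroids". For Grade 3 rash it tells the investigator to "consider oral prednisolone at a dose of 0.5 mg/kg". None of these refers to Section 6.5.2 or states an exemption.

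**The DLT rules.** Section 6.6.2.2 states: "The DLT window of observation will be during first 21-days of treatment". Criterion 8 counts as a DLT "Any treatment-related toxicity that causes the participant to discontinue treatment during Cycle 1". Section 5.6 treats as nonevaluable, and replaces, a participant who leaves before the safety evaluations are complete for a reason that is not a treatment-related AE.

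**The concern.** A site that gives antiemetic dexamethasone follows Section 6.5.3.1 and at the same time uses a drug that Section 6.5.2 bars. Two sites with the same patient could act differently, and both could point to the protocol.

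This would be a minor drafting matter if it stayed within concomitant-medication reporting. It can reach the primary endpoint because the mTPI rule acts on very small counts. A participant removed in Cycle 1 over a barred steroid may be entered as a DLT, or dropped from the denominator and replaced; a participant who stays on treatment is evaluable without a DLT. Discontinuation of study drug due to an AE is also a primary endpoint (Section 3), and it inherits the same uncertainty about whether the AE or the prohibited drug was the reason.

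**Working it through.** **Step 1. Does the exception in Section 6.5.2 cover the suggested uses?**

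- *Dexamethasone as antiemetic.* Preventing or treating selumetinib nausea is not treatment of a suspected immunologic AE. The physiologic-dose allowance needs sponsor agreement, which the nausea text does not mention. The use is therefore outside both allowances, and Section 6.5.1 does not lift the ban.
- *Prednisolone and low-dose systemic corticosteroids for rash.* Section 6.5.3.1 presents the skin measures as additions to the rash guidance in Table 5, the immune-related AE table. Section 6.6.1 lists skin rash among the overlapping toxicities and says "the relationship of these AEs to selumetinib and/or pembrolizumab may be difficult to unambiguously assign". Rash of suspected immunologic origin is inside the exception. The conflict remains for rash judged not immunologic.

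**Step 2. What follows if a participant is removed in Cycle 1?**

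- If treatment-related nausea is held to be the cause, criterion 8 applies: DLT.
- If the prohibited drug is held to be the cause, Section 5.6 applies: nonevaluable, replaced.
- If the participant is not removed, and has no other DLT: evaluable without a DLT.

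No sentence says which of the first two applies. Removal after day 21 does not affect the count.

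A drug-related Grade 3 rash treated with corticosteroids in the window is a separate case. Section 6.6.2.2 excepts Grade 3 rash only when corticosteroids or anti-inflammatory agents are not used, so it is a DLT whether or not the participant is removed.

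**Step 3. Reproduce Table 1.** Inputs from Section 4.3.1.4: target 0.30, Beta(1,1) prior, ε1 = ε2 = 0.03. With x DLTs in n participants the posterior is Beta(1+x, 1+n−x). The decision is the interval with the largest posterior mass divided by width, over (0, 0.27), (0.27, 0.33) and (0.33, 1). DU is assigned if P(rate > 0.30) exceeds 0.95; that cutoff is an assumption, as the documents do not state it.

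| x/n | E: mass/0.27 | S: mass/0.06 | D: mass/0.67 | P(rate > 0.30) | Decision |
|---|---|---|---|---|---|
| 0/3 | 2.652 | 1.375 | 0.301 | 0.240 | E |
| 1/3 | 1.096 | 1.760 | 0.893 | 0.652 | S |
| 2/3 | 0.233 | 0.756 | 1.331 | 0.916 | D |
| 3/3 | 0.020 | 0.109 | 1.475 | 0.992 | DU |

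All 78 legible cells in rows 0 to 6 agree with Table 1. Rows 7 and 8 are broken in the text available and were not compared.

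**Step 4. Classify one participant three ways.** The first column gives the DLTs among the other members of the cohort.

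| DLTs among the others | Retained, no DLT | Counted as DLT | Nonevaluable, before replacement |
|---|---|---|---|
| 0 of 2 | 0/3 E | 1/3 S | 0/2, below the minimum of 3 |
| 1 of 2 | 1/3 S | 2/3 D | 1/2, below the minimum of 3 |
| 2 of 2 | 2/3 D | 3/3 DU | 2/2, below the minimum of 3 |
| 1 of 3 | 1/4 S | 2/4 S | 1/3 S |
| 2 of 3 | 2/4 S | 3/4 DU | 2/3 D |
| 1 of 5 | 1/6 E | 2/6 S | 1/5 S |
| 3 of 5 | 3/6 S | 4/6 DU | 3/5 D |

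Across rows 0 to 6, moving down one row (one more DLT, same n) changes 27 of 66 decisions. This is an unweighted count of cells, not a probability.

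**The case against.** Much of the case on the other side stands.

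- **A reader might infer that the two sections cannot both be followed.** They can: dexamethasone is one of five named antiemetics, offered as needed, and a site using any of the other four complies with both. What cannot be reconciled is the dexamethasone option itself.
- **A reader might infer that giving the steroid triggers removal.** Section 6.5.2 attaches removal to the investigator's judgment that the treatment is required. Choosing one of several options does not establish that.
- **A reader might infer that the rash steroids distort the DLT count in the same way.** Some of that use is covered by the immunologic exception, and drug-related Grade 3 rash treated with corticosteroids in the window counts as a DLT regardless. The route to the count is mainly antiemetic dexamethasone.
- **Criterion 8 and Section 5.6 are largely complementary.** One concerns treatment-related toxicity, the other reasons apart from it. If dexamethasone is given before any nausea, there is no toxicity for criterion 8 to act on. The ambiguity is confined to the participant with treatment-related nausea who takes a barred drug and is removed in Cycle 1.
- **A reader might assume a rate of steroid use and compute how many cohorts would be affected.** The documents give no such rate. The result would be the chance of any exposure, not of a changed decision, which also needs a judgment that the drug was required, removal within 21 days, classification under criterion 8 and no other DLT.

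These points narrow the concern. They do not supply an exemption for dexamethasone or a classification rule.

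**Conclusion.** The contradiction is real. It is clear for antiemetic dexamethasone and conditional, on the rash not being suspected immunologic, for prednisolone and low-dose systemic corticosteroids. A Cycle 1 removal on this ground can alter the DLT count; the documents do not support saying that it will.

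Where it occurs, counting the participant as a DLT changes every decision short of DU at n = 3 (E to S, S to D, D to DU). Counting the participant as nonevaluable leaves a cohort of 3 without a decision until replacement. In larger cohorts some decisions change and others do not. The frequency cannot be derived, and none is offered here.

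The size rests on Table 1 as printed. The 0.95 DU cutoff was assumed only to reproduce the table, and the shifts quoted can be read from the printed cells without it.

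**What to change.** 1. Reconcile Section 6.5.2 with the nausea, skin toxicity and Grade 3 rash text of Section 6.5.3.1, so that the same steroid use is not both suggested and grounds for removal. The clinical choice is the sponsor's.
2. Bring Section 6.5 into the same reconciliation. It requires discontinuation of study intervention when a medication prohibited by the exclusion criteria is indicated, and exclusion criterion 7 concerns systemic steroids. Section 6.5.2 speaks of removal from the study, while Section 7.1 says that discontinuing intervention is not withdrawal. State which consequence is meant.
3. State in Sections 5.6 and 6.6.2.2 how a Cycle 1 removal for a prohibited steroid is classified (DLT, or nonevaluable and replaced) and on what basis the cause is assigned, so that all sites count alike. Apply the same rule to the endpoint of discontinuation due to an AE.

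The cost is a wording amendment. Table 1, the sample size and the assessment schedule are unaffected, and concomitant medication is already recorded under Section 6.5.1.

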## 6.5.3 Supportive Care

### 6.5.3.1 Selumetinib Supportive Care Guidelines

#### Hypertension

It is recommended that additional blood pressure monitoring occur for participants who may be at risk (participants with hypertension at baseline) or those with antecedents of hypertension or those treated with antihypertensive medication. Early initiation of treatment is recommended after diagnosis, with aggressive management of emergent hypertension.

#### Nausea and/or vomiting

Because nausea and vomiting have been reported for selumetinib, it is recommended that participants are educated on the possibility of occurrence of these side effects prior to starting study treatment. Participant education as well as proper management of nausea and/or vomiting at the first sign is important. Clinical judgment and experience of the treating physician should guide the management plan of each participant. Participants experiencing nausea and/or vomiting CTCAE Grade  $\geq 1$  should receive antiemetics at the discretion of the treating physician (as per local guideline). It is recommended that participants be provided a prescription for antiemetics and are instructed on the use of antiemetics on the first day of study drug treatment. Prophylactic antiemetics such as dexamethasone 8 mg, prochlorperazine, metoclopramide, ondansetron, or aprepitant may be administered to participants on an "as needed" basis. Medication use should be recorded accordingly.

Dose interruption/reduction decisions for nausea and/or vomiting should be based on the CTCAE grade of the toxicity and the guidelines provided in Section 6.6.1.

As guidance for recommendations on supportive measures for the prevention and/or management of nausea and/or vomiting, the published recommendation from ASCO [Sepulveda, A. R., et al 2017], ESMO [Van Cutsem, E., et al 2016], and Multinational Association of Supportive Care (MASCC) can be used [Basch, E., et al 2011] [Roila, F., et al 2010].

